Statistical Analysis Plan

A Trial of Online LGBTQ-affirmative Cognitive Behavioral Therapy to Reduce Depression and Associated Health Risks Among Young Adults
NCT04408469

01/18/2023

Intervention efficacy will be assessed using an intent-to-treat analysis and include all participants (n = 120). First, dependent variables and stigma moderators will be assessed for normality using skewness thresholds of ≥ 2 and kurtosis thresholds of ≥ 7 . If scales violate assumptions of normality, they will be square root transformed.

To examine the efficacy of LGBTQ-affirmative ICBT, we will use linear mixed models with maximum likelihood estimation and an unstructured covariance matrix to test the Condition × Time interaction effects between conditions over time for all continuous mental health outcomes (BSI, CESD, ODSIS, OASIS). For binary outcomes (suicidal thoughts, problematic drinking, SIDAS, sex-risk behavior), we will test intervention efficacy using a generalized linear mixed model with a logit link and a binomial distribution to test the Condition × Time effect predicting odds of each binary outcome between conditions over time. Primary efficacy analyses between conditions will include baseline (time = 0), immediate post-intervention (time =1), and 4-month follow-up (time = 2) to model the Condition × Time effect of receiving LGBTQ-affirmative ICBT (condition = 1) versus self-monitoring (condition = 0). Effect sizes (Cohen's d) for linear mixed models will be calculated as mean pre-post change (e.g., pre-intervention to post-intervention, pre-intervention to 4-month follow-up) in the LGBTQ-affirmative ICBT intervention minus the pre-post change in the self-monitoring condition, divided by the pooled baseline standard deviation.

To examine whether Condition × Time effects varied as a function of baseline levels of heterosexist stigma (i.e., internalized stigma, interpersonal stigma, and structural stigma), we will conduct moderation analyses using linear mixed models with maximum likelihood estimation, unstructured covariance matrix, and three-way interactions of Condition × Time × Stigma.

Moderation by internalized, interpersonal, and structural stigma will be entered together into

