multivariable models for each outcome. Significant three-way interactions of Condition \times Time \times Stigma will be further probed and plotted to contrast high stigma (one standard deviation above the mean) with low stigma (one standard deviation below the mean). All results will be evaluated at p < .05.

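### Aim 2 moderation: 12 interaction tests fitted by maximum likelihood and each judged at p < .05, with no small-sample correction and no exploratory label

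*SAP*

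**What the plan says.** The Protocol's Statement of Purpose sets two questions for the trial: whether online EQuIP improves mental health more than self-monitoring, and whether participants with more LGBTQ-specific stress at baseline benefit more.

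The SAP answers the second in one paragraph: "we will conduct moderation analyses using linear mixed models with maximum likelihood estimation, unstructured covariance matrix, and three-way interactions" of condition, time and stigma. Internalized, interpersonal and structural stigma go in together, in "multivariable models for each outcome". Significant three-way terms "will be further probed and plotted to contrast high stigma (one standard deviation above the mean) with low stigma" one standard deviation below the mean. The closing rule is "All results will be evaluated at p < .05".

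The efficacy paragraph assigns linear mixed models to "all continuous mental health outcomes (BSI, CESD, ODSIS, OASIS") and, for four binary outcomes, a "generalized linear mixed model with a logit link and a binomial distribution". It codes the three visits 0, 1 and 2. Neither document mentions a multiplicity adjustment, a lead moderation test, an exploratory status for moderation, or a reference distribution for the mixed-model tests.

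The Protocol (Targeted Enrollment, derivation of the estimate) sizes the trial for the difference in depressive symptoms, with 60 per arm and 25% attrition. It gives no power for moderation.

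**The concern.** Two features of the rule make an Aim 2 result hard to read.

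First, a set of interaction tests is judged at the same threshold as the main efficacy tests, and nothing says how much weight one significant term should carry. With 12 looks, an isolated p < .05 is a likely chance event. With a sample sized for a main effect, a p above .05 says little either. The practical risk is a claim that the treatment works better, or no better, for people under more stigma, when the data cannot support either statement.

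Second, maximum likelihood estimates variances as if the fixed effects were known. The standard errors are then too small, and more so as fixed effects are added. The moderation model has four times as many as the efficacy model, so the distortion is greatest where the evidence is thinnest.

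**Working it through.** **1. The plan's own sample size.** Inputs from the Protocol: effect 0.61 (the smallest of the three cited), power 80%, alpha .05 (two-sided assumed), attrition 25%.

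- n per arm = 2 × (1.96 + 0.8416)² / 0.61² = 42.2, so 43. Then 43 / 0.75 = 57.3, so 58.
- A t-test version gives 44, and 44 / 0.75 = 58.7, so 59.

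The stated 60 per arm is reproduced to within 2. It leaves 45 completers per arm, with power about 0.82 for the main effect.

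**2. Number of moderation tests.** Four continuous scales × three stigma types × one condition-by-time-by-stigma test each = 12. The count is the same if time is a factor and each stigma type gets one joint two-degree-of-freedom test per scale.

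**3. False positives if there is no moderation.**

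- Expected number: 12 × 0.05 = 0.6.
- At least one, independent tests: 1 − 0.95¹² = 0.460.
- At least one, correlated tests. The documents give no correlations, so these are assumptions. Stigma measures correlated .3 and entered together give coefficient correlations of −.3 / 1.3 = −.231. With 300,000 draws:

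| Correlation between outcomes | Chance of at least one p < .05 |
|---|---|
| 0 | .449 |
| .3 | .424 |
| .5 | .388 |
| .7 | .332 |

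**4. Power for one interaction.** Assume the treatment effect changes by 0.3 SD per SD of stigma (the documents give no figure), with 90 completers. Three moderators correlated .3 inflate the variance by 1.161. For a baseline-to-visit contrast with visit correlation r:

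SE = √[2(1 − r) × 1.161 / (90 × 0.25)]

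- r = .4, .5, .6 gives SE .249, .227, .203 and power .226, .262, .315.
- Using the 30 baseline-only participants as well gives power .241 to .328. Overall this is 23 to 33%.
- With a linear time term, power is about 20 to 36% if the effect holds or builds steadily.
- 80% power for a visit contrast needs roughly 0.55 to 0.70 SD per SD of stigma.

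**5. Effect of maximum likelihood.** With all lower-order terms and linear time, the moderation model has 2 × 2 × 4 = 16 fixed effects (24 with time as a factor). The efficacy model has 2 × 2 = 4 (or 6).

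Hand check on 90 completers' change scores. There are 2 × 4 = 8 between-person terms, leaving 82 degrees of freedom. ML shrinks the standard error by √(82/90) = 0.955, so the nominal 1.96 acts as 1.96 × 0.955 = 1.871. On t with 82 df that is an error rate of 6.5%. Using the t critical value 1.989 instead gives 1.989 × 0.955 = 1.899, or 6.1%.

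Simulation of the mixed model: N = 120, 30 with baseline only, unstructured covariance, assumed visit correlations .45, .40 and .65, t with 82 df (moderation) or 88 df (efficacy), 5,000 replicates, Monte Carlo SE 0.31 points. Type I error per test, in %:

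| Model | ML, z | ML, t | REML, z | REML, t |
|---|---|---|---|---|
| Moderation, linear time | 6.9 | 6.4 | 5.7 | 5.3 |
| Moderation, post-treatment contrast | 6.9 | 6.7 | 5.8 | 5.4 |
| Efficacy, linear time | 5.6 | 5.2 | 5.2 | 4.9 |
| Efficacy, post-treatment contrast | 5.6 | 5.3 | 5.3 | 5.0 |

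Repeat runs gave 6.4 to 6.9% for ML with z and 5.3 to 5.6% for REML with t in the moderation model.

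**6. The two together.** For 12 independent tests at the simulated ML-z rate, 1 − (1 − 0.0686)¹² = 57%. At the REML-t rate, 1 − (1 − 0.0526)¹² = 48%. REML removes the estimation excess but not the multiplicity.

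**The case against.** The best defence is that moderation is plainly secondary. The Protocol names depressive symptoms as the primary aim, introduces both questions as an evaluation of preliminary efficacy, and the SAP reserves the word primary for the efficacy analyses. Leaving secondary moderation tests unadjusted in such a trial is common practice. That stands, and it is why no adjustment is asked for. It does not supply the missing label, and the closing rule applies one threshold to everything.

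It is also fair that the ML effect is modest, that a normal reference has to be assumed, and that the 0.3 SD used for power is arbitrary.

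A reader might infer more than the documents support:

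- **24 or 48 tests.** These counts need the four binary outcomes to be included, or each follow-up visit to be tested separately. The SAP pairs linear mixed models with the continuous scales and names only that model for moderation. The by-visit changes, "mean pre-post change (e.g., pre-intervention to post-intervention, pre-intervention to 4-month follow-up"), define an effect size, not a second test. The phrase about each outcome is loose, but 12 is the natural count.
- **Failure of logistic models for rare outcomes.** The SAP names no logistic model for moderation, and the documents give no prevalences.
- **Very low power because a linear time term misses a fading effect.** That requires an assumed fading pattern, and the documents state no such hypothesis.
- **Selective reporting.** Only probing and plotting depend on significance. Nothing says that other interactions go unreported.

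**Conclusion.** The concern holds in limited form. Under the rule as written, and with no true moderation, the plan has a 46% chance (independent tests) or about 33 to 45% chance (assumed correlations) of at least one significant interaction among 12. Power for a moderate interaction is low, on an assumed effect size. One significant term should not be read as confirming moderation, nor a non-significant one as excluding it.

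ML without small-sample degrees of freedom raises per-test error to about 6.5 to 7% with z, or about 6 to 6.7% with t, against about 5.3% for REML with t. These figures rest on 25% attrition, the assumed visit correlations, and inclusion of all lower-order terms.

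The primary comparison is barely touched: the same change is worth about 0.6 to 0.7 points there. The point deserves a change because both remedies alter a stated rule at almost no cost.

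**What to change.** 1. In the linear mixed models, replace maximum likelihood with REML and use Kenward-Roger or Satterthwaite degrees of freedom. The gain is about 1.5 points of per-test error for moderation relative to ML with z, and small for efficacy. It is a standard software option.
2. State that the Aim 2 moderation results are exploratory. Report all three-way interaction estimates with confidence intervals, whether or not significant; probing and plotting can stay as planned.
3. As minor clarification only, state that moderation covers the four continuous scales and whether time enters as a slope or a factor.

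No new data are needed. The downside is that Aim 2 can yield no confirmatory claim, which the sample size would hardly have supported in any case.

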unique strengths. In a preliminary trial of an in-person intervention delivered to young adult gay and bisexual men (*n*=63), this intervention significantly reduced participants spectrum of interrelated health threats, making it the first evidence-based intervention to simultaneously improve mental health, substance use, and sexual health outcomes among young adult gay and bisexual men. Two ongoing RCTs are ongoing, including one waitlist trial that extends to women this first trial delivered to men and one that represents a larger extension of the original waitlist trial with men. We are confident that our revised treatment applies to all genders because we have conducted formative qualitative interviews with all genders to ensure the treatment's relevance. Also, our first trial was limited to men only because of gender inequities in NIH funding for LGBTQ-focused research, in which the majority of funding is devoted to research pertaining to gay and bisexual men rather than sexual minority women.

Because this treatment has only been tested using an in-person treatment in NYC and Miami, this precludes reaching LGBTQ young adults across geographic locales, including those locales that might not provide LGBTQ-affirmative brick-and-mortar services. Therefore, we propose to test an online version of EQuIP in high-stigma, low-resource geographies across the US. At the same time, whether LGBTQ-specific adaptations are required for treatment efficacy remains unknown. Perhaps standard CBT that does not include LGBTQ-specific adaptations are equally efficacious, which would provide the treatment field with essentiall guidance, including whether existing (non-LGBTQ-adapted) treatments can be distributed to LGBTQ youth in need.

To evaluate the preliminary efficacy of an LGBTQ-affirmative online CBT treatment and whether such an LGBTQ-affirmative focus adds benefit, we propose a 2-arm RCT that would examine (1) whether online EQuIP demonstrates significant mental health improvements compared to self-monitoring of stress and mood, and (2) whether participant baseline LGBTQ-specific stress exposure moderates treatment efficacy, such that participants with the most LGBTQ-specific stress exposure benefit more from online EQuIP than self-monitoring of stress and mood."

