Our primary outcomes are depressive symptoms, anxiety symptoms, substance abuse, sexual risk behavior, and suicidality, all of which disproportionally affect LGBTQ young adults. Secondary outcomes include hypothesized cognitive, affective, and behavioral minority stress mechanisms, such as internalized homophobia, rejection sensitivity, concealment, social isolation, and emotional dysregulation.

In preparation for this RCT, we will deliver the online EQuIP treatment to 14 LGBTQ young adults who meet all eligibility criteria for the full trial. The purpose of this initial test is to ensure acceptability of the treatment content and usability of the technical platform.

2. **Background:** Describe the background information that led to the plan for this project. **Provide** references to support the expetation of obtaining useful scientific data.

Clear and consistent evidence now suggests that LGBTQ young adults disproportionately experience depression, anxiety, suicidality, substance abuse, and sexual risk compared to heterosexual, cisgender individuals. Diverse methods locate the source of these disparities in LGBTQ young adults' exposure to minority stress—the stress associated with stigma-related social disadvantage. In fact, minority stress, mental health problems, substance use disparities, and sexual

Page 3 of 22

risk fuel each other, forming a synergistic threat to LGBTQ young adults' health. Yet, until our team's work, no existing evidenced-based intervention existed to addresses minority stress and its impact on LGBTQ young adults' mental and behavioral health.

Minority stress theory suggests that stigma compromises LGBTQ young adults' mental, behavioral, and sexual health health through several cognitive, affective, and behavioral pathways. These pathways emerge early in development and include negative thinking styles, unhealthy emotion regulation habits, low behavioral self-efficacy, and behavioral avoidance. Some of these processes are LGBTQ-specific, such as internalized homophobia and expectations of LGBTQ-related rejection; others are universal but elevated among LGBTQ young adults, such as low self-worth and unassertiveness. All are related to poor mental health, suicidality, substance abuse, and sexual risk. Our conceptual model suggests that an intervention that reduces these minority stress processes could simultaneously improve the full spectrum of LGBTQ young adults' mental and behavioral health risks.

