homework reviews. Therapists will either be postdoctoral fellows in the [name] lab or clinical/counseling psychology interns/externs in the [name] lab who possess an advanced degree in a mental health field with significant prior experience treating LGBTQ young adults with mental health concerns. Modules were adapted directly from the inperson materials (e.g., therapist manual, participant handouts) used in our previously successful trials of this treatment. A team of six therapists and supervisors of the original in-person treatment adapted the text for the online modules, including realistic vignettes and easy-to-follow skills training. A video production company created accompanying videos with our clinical team's close input.

At baseline, immediately post-treatment (4-month followup), and 8-month followup, participants will complete online surveys assessing their mental and behavioral health. Automatically generated alerts will immediately be sent to project staff in response to a participant indicating suicidality in response to suicidality assessments, at which point the study staff will implement the cinical protocol.

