After completing the baseline assessment, participants will be assigned a study therapist and will be contacted by their therapist to schedule a 30-minute introductory call via Zoom video conferencing or telephone. During this conversation, therapists will explain the structure of the study and briefly discuss the participant's motivations and goals for participating in the study. Participants will then complete one session (self-monitoring, online EQuIP, or enhanced online EQuIP) per week. If participants miss a session, as determined by daily therapist and RA review of session access and self-monitoring or homework completion, they will receive a reminder to complete the session. Participants will also be asked to schedule a check-in phone call with their study therapist two-weeks post-randomization to discuss their progress through the study sessions. Participants will have a window period of four months to complete all 10 sessions. At 8-month followup, 20 participants randomized to the Online EQuIP condition who completed the treatment will be contacted and invited to participate in a 45-60 minute phone interview. The purpose of this phone interview is to ask participants to answer questions in regard to their experience in completing the treatment (e.g., things they liked, things they did not like, things they would change).

Before we randomize participants into the full trial, we will pilot-test the online EQuIP treatment with 14 LGBTQ young adults who meet all eligibility criteria planned to be employed for the full trial. In addition to completing 10 online EQuIP sessions, these participants will complete baseline and immediate post-treatment (3-month followup) assessments as well as a qualitative interview about their experience at 3-month followup. These participants will not complete any additional follow-up assessment.

4. **Participant Population:** Provide a detailed description of the types of participants who will be recruited into this study.

Inclusion criteria. Eligible participants will meet the following criteria: (1) aged 16-25, (2) identify as lesbian, bisexual, gay, or another sexual minority identity (e.g., pansexual, demisexual) (3) pastweek symptoms of depression or anxiety using the Brief Symptom Inventory-4 cutoff of 2.5 on either the depression subscale or anxiety subscale; (4) weekly access to internet on a laptop, desktop,

Page 5 of 22

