4) Peer-recruitment and referrals by previous and current study participants. Participants in the study will be asked to distribute study recruitment materials to peers who may be interested in participating in the study. Participants will be reminded that staff will never disclose any information about an individual's participation in the study, but that participants are free to disclose information about their own participation to whomever they desire. Participants are not required to distribute recruitment materials as a condition of study participation and the strictly voluntary nature of this request will be emphasized by study staff.

Recruitment text and images are attached to this application.

Are you collecting any information about the individuals prior to their signing a consent form? Yes \square No \boxtimes

If yes, indicate what information you will be collecting and how it will be gathered *(phone screen, paper questionnaire, etc.)*

2. **Indicate recruitment methods below.** Attach copies of any recruitment materials that will be used.

\boxtimes	Flyers	🛛 In	ternet/Web Postings	Radio
	Posters	$\boxtimes M$	ass E-mail Solicitation	🛛 Telephone
_	Letter		epartmental/Center Website	Television
imes	Newspaper			
\boxtimes	Through local NGO or other local conta	act	Social Media (Facebook, Twitter	ſ)
	Classroom recruitment			
	Table set-up / in-person recruitment of	public		
imes	Snowball sampling			
	Other (describe):			

3. Targeted Enrollment: Give the number of participants:

- a. Targeted for enrollment for this protocol: 120 (plus an additional 14 participants who will pilot the study)
- b. If this is a multi-site study, give the total number of participants targeted across all sites: N/A

4. How was this estimate derived?

We aim to recruit 120 participants into this study. Our primary aim is to demonstrate a greater reduction in 4-month follow-up in depressive symptoms in the online EQuiP condition compared to the self-monitoring control. Using a 1:1 randomization, we will randomly assign 60 participants to each of the two conditions (i.e., online EQuIP and the self-monitoring control). Assigning 60 participants into each condition will allow us to detect a difference ($\beta = 0.2, p < .05$) consistent with the average effect of online CBT involving therapist support (compared to a weak control condition) found across meta-analyses of online CBT: .61 (Andersson & Cuijpers, 2009), .83

Page 8 of 22

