(Sztein, Koransky, Fegan, & Himelhoch, 2018), and 1.00 (Spek, Cuijpers, et al., 2007). This estimate accounts for 25% attrition at 3-month follow-up, consistent with the attrition rate in our current in-person treatment study of 254 young gay and bisexual men and exceeding that found in our previous online intervention research (e.g., [name] & Goldfried, 2010).

Before we randomize participants into the full trial, we will pilot-test the online EQuIP treatment with 14 LGBTQ young adults who meet all eligibility criteria employed for the full trial. The purpose of this initial test is to ensure acceptability of the treatment content and usability of the technical platform.

5. **Process of Consent/Assent** (*NOTE: When a study includes minors, parent provide permission [not consent] for the child's participation, and the child provides assent for participation)*

Describe the setting and conditions under which consent/assent will be obtained, including parental permission or surrogate permission and the steps taken to ensure participants' independent decision-making.

Informed consent will be obtained for all participants at three points – before completion of the online screener, phone screener, and baseline survey.

Before completing the online screener, participants will review an online consent form describing the screening purpose and risks/benefits and indicate their consent by selecting the commensurate button. Participants' identifying information, including their name, will be kept in a separate database from the remainder of their study responses. Participants who are deemed preliminarily eligible based on the online screener will be contacted by our study staff to confirm eligibility by phone screen.

Before administering the phone screener, a project staff member will first assess participants' willingness and capacity to consent to completing the screener to determine eligibility. Participants will provide their verbal consent for the phone screener. Participants' identifying information, including their name, will be kept in a separate database from the remainder of their study responses.

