The full packet of study measures and assessments is attached to this application. We propose to collect information about participants' general mental health status, including demographics; depressive and anxious symptoms and suicidality; substance use; sexual-risk behavior; HIV status; experiences with stigma-related stress; cognitive, affective, and interpersonal functioning (e.g., rumination, social support, impulsivity, assertiveness); mental health treatment history and perspectives; and perceptions of intervention helpfulness. For participants in the active treatment conditions (online EQuIP), we will also collect participants' homework assignment text regarding the above topics and therapists' homework feedback. Therapists will document all phone contact on a password-protected file stored on Yale's HIPAA-compliant Secure Box.

Participants will provide the following data at baseline, 4-month (immediate post-treatment) followup, and 8-month follow-up appointments: quantitative assessments, previously used with LGBTQ young adults, of mental health, suicidality, substance use, sexual-risk behavior, and stigma-related stress, and (at 4- and 8-month follow-ups only) intervention acceptability.

Page 12 of 22

The 20 participants from the Online EQuIP condition will provide feedback in regard to their experience in completing the treatment (e.g., things they liked, things they did not like, things they would change). Pending consent from participants, these interview will be audiorecorded.

The 14 participants who will take part in the initial pilot trial will complete baseline and immediate post-treatment (3-month followup) assessments as well as a qualitative interview about their experience at 3-month followup. These participants will not complete the 6-month followup assessment.

2. Will any of the following identifiers be collected?

Names 🛛

All geographic subdivisions smaller than a State, including: street address, city, county, precinct, zip codes

 \boxtimes Telephone numbers

Fax numbers

 \boxtimes E-mail addresses

Social Security numbers

Medical record numbers

Health plan beneficiary numbers

Account numbers

 \square All elements of dates (except year) for dates related to an individual, including: birth date, admission date, discharge date, date of death, all ages over 89 and all elements of dates (including year) indicative of such age, except that such ages and elements may be aggregated into a single category of age 90 or older

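### The protocol lists five primary outcomes but powers one depression aim, and the SAP tests eight outcomes and stigma moderation at p < .05 without naming a primary test

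*SAP*

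**What the plan says.** Protocol, Statement of Purpose: "Our primary outcomes are depressive symptoms, anxiety symptoms, substance abuse, sexual risk behavior, and suicidality". The list is not ranked. The same section makes moderation its second aim: "whether participant baseline LGBTQ-specific stress exposure moderates treatment efficacy".

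Protocol, Section V, item 4: "Our primary aim is to demonstrate a greater reduction in 4-month follow-up in depressive symptoms". The sample size of 60 per arm serves this one comparison, with beta = 0.2 and p < .05. It cites effects of .61, .83 and 1.00 and adds "This estimate accounts for 25% attrition at 3-month follow-up". No instrument is named.

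SAP, main text: Condition × Time is tested on four continuous outcomes (BSI, CESD, ODSIS, OASIS) and four binary ones (suicidal thoughts, problematic drinking, SIDAS, sex-risk behavior). The three-time-point analyses are labelled primary without singling out an outcome or a contrast. Three stigma measures (internalized, interpersonal, structural) then enter together in three-way interaction models for each outcome. The closing rule is "All results will be evaluated at p < .05".

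Visits: the protocol's Research Plan assesses participants "At baseline, immediately post-treatment (4-month followup), and 8-month followup", and Section VI, item 1 agrees. In the SAP, immediate post-intervention is time = 1 and the 4-month follow-up is time = 2.

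**The concern.** The power statement cannot be matched to one analysis. The two protocol passages disagree on what is primary, and the SAP settles neither the scale nor the contrast. A reader of the results could not tell the planned positive finding from the most favourable of several. The moderation tests raise the same problem, because they answer a stated aim with three interactions per outcome and no rule for what counts as support.

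The SAP cannot show by itself that a later choice of scale or contrast preceded the data. It is dated 01/18/2023, and Section VIII, item 2 of the protocol expects the last follow-up in February 2022, about 11 months earlier.

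**Working it through.** **1. Reproduce the plan's sample size.** Inputs from Section V, item 4: d = 0.61 (the smallest cited effect), 80% power, alpha .05, 25% attrition. Two-sided testing is assumed because sidedness is not stated.
- A two-sample t-test needs 44 completers per arm, and 44 / 0.75 = 58.7, so 59 randomized against 60 stated. The figure reproduces for one test.
- With 60 × 0.75 = 45 completers per arm, power is 82%.

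**2. Count the tests.**
- Protocol primary outcomes: 5.
- SAP outcomes: 4 + 4 = 8.
- Moderation: 3 stigma measures × 4 continuous outcomes = 12, since linear mixed models are specified. It is 3 × 8 = 24 if the binary outcomes are included.
- Candidate depression scales: 2, assuming that CESD and ODSIS are both depression measures, which the documents do not state. BSI is left out because the SAP does not say how it is scored.

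**3. Chance of at least one false positive when every null is true.** For m independent tests this is 1 − .95^m. The correlated figures assume equicorrelated normal statistics; the documents give no correlations.

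| Set | m | Independent | r = .5 | r = .7 | r = .9 |
|---|---|---|---|---|---|
| Two depression scales | 2 | 1 − .95² = 9.8% | – | 8% | 7% |
| Protocol's five, one test each (assumed) | 5 | 1 − .95⁵ = 22.6% | 18% | 15% | 10% |
| SAP's eight | 8 | 1 − .95⁸ = 33.7% | 25% | 19% | 12% |

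**4. Moderation.** Independence gives 1 − .95¹² = 46.0% for 12 tests (1 − .95²⁴ = 70.8% for 24). Equal positive correlation among all 12 statistics is not a suitable model, because the three moderators are adjusted for one another. By simulation, with correlation only across the four outcomes, the 12-test rate is about 40% at r = .5 and 34% at r = .7 for uncorrelated moderators. With moderators correlated .4 (assumed), it is about 38% and 33%.

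**5. Power of one designated test.** Inputs: n = 45 per arm, d = 0.61 in baseline-SD units, equal SDs, and r the baseline-to-follow-up correlation (assumed).
- Change score: effect 0.61 / √(2(1 − r)). At r = .3 this is 0.61 / √1.4 = 0.516, with power 68%. At r = .5 and .7, power is 82% and 96%.
- Mixed model with unconstrained baseline means, 60 baseline and 45 follow-up values per arm: variance per arm (1 − r²)/45 + (1 − r)²/60, with power 72% at r = .3.
- Baseline-adjusted: effect 0.61 / √(1 − r²). At r = .3 this is 0.61 / √.91 = 0.639, with power 85%.

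**6. Power if alpha is split instead** (two-sample t-test, 45 per arm). Five outcomes at .01 each give 60%, and 80% would need 65 / 0.75 = 86.7, so 87 randomized per arm. Eight outcomes at .00625 each give 54%, and 80% would need 71 / 0.75 = 94.7, so 95 per arm.

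**The case against.** The best reply is that the hierarchy is already there. Section V, item 4 states one primary aim with a domain, a time and a comparator, and the SAP's title puts depression ahead of associated risks. On that reading only the scale and the contrast are open, and the relevant error rate is the 7–10% for two scales. This stands in part: it is a reason to make depression the primary. It does not close the point, because the Statement of Purpose still lists five primaries and the SAP does not carry the single aim into its tests.

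A reader might infer that this trial's false-positive rate is 23%, 34% or 46%. The documents do not support that. Those figures need a rule that any one significant result counts as success, and neither document states one. A claim about one outcome fixed in advance keeps its 5%.

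A reader might also infer from the SAP's date that outcomes were chosen with the data in view. The end of follow-up is a projection, and the date shows neither data access nor the absence of an earlier plan. The attached measures packet is not among the documents either, so the gap is established for these two documents only.

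Finally, the Statement of Purpose speaks of preliminary efficacy. That softens the claims but does not remove a powered primary aim at p < .05.

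**Conclusion.** The point holds. These two documents conflict on what is primary and designate no test to carry the trial-level 5%. The smallest version of the problem, depression only with two candidate scales, gives 7–10%. That range counts one test per scale, so it does not cover an open choice of contrast. The larger figures are upper values that apply only if a claim may be picked from the five outcomes, the eight outcomes or the 12 interactions. All of them rest on the global null and two-sided tests, and the ranges rest on assumed correlations.

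The sample size is not in error: 60 per arm reproduces for one two-sided test at .05. What is missing is the identity of that test.

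**What to change.** - **Primary.** Reconcile the Statement of Purpose with Section V, item 4 by making depressive symptoms at the protocol's 4-month immediate post-treatment visit (SAP time = 1) the single primary, with one named scale and one named contrast at two-sided .05.
- **Estimation.** Take the contrast from the planned mixed model, preferably with baseline adjustment or a common baseline mean. At r = .3 this gives about 85% power, against 68–72% for an unconstrained change contrast.
- **Provenance.** Cite a pre-data record for both the scale and the contrast. If there is none, disclose that both were set in a SAP dated after the projected end of follow-up, and also apply Holm across the candidate depression scales. Holm over scales does not replace disclosure of the contrast.
- **Other analyses.** Label the remaining outcomes secondary (for example, Holm-adjusted after the primary) or exploratory with unadjusted intervals. Label stigma moderation secondary or exploratory.
- **Visit names.** The SAP's time = 2 visit appears to be the protocol's 8-month visit, since the protocol says "Participants will have a window period of four months to complete all 10 sessions" and places its 4-month assessment at the end of treatment. Align the labels, and reconcile the 3-month attrition figure in Section V, item 4.

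Cost: no added participants or data. The demoted outcomes and moderation tests carry weaker claims, and the later visit leaves the primary test. If Holm is needed across two scales, the first step is at .025. Per-scale power at r = .3 is then about 57% for a simple change score and, with the 0.639 effect above and 45 per arm, about 77% with baseline adjustment.
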